## **7.2 Group 1: Baseline and Treatment Phase Study Activities (Subjects Participating in the MWT Component of the Study)**

IF THE SUBJECT IS NOT IN GROUP 1, GO TO [SECTION 7.3](#).

### **7.2.1 Group 1: Baseline/Randomization/Visit 2 (Day -2 to -1)**

After a subject has successfully completed the screening procedures he or she will return to the investigative site to complete his or her baseline procedures. The subject may be admitted to the study center the day before (Day -2) the MWT to complete selected assessments provided that it falls within the visit window (listed in [Appendix 2](#)). Individual assessments should be performed on the same study day at approximately the same time of day across study visits.

On admission to the study center in the morning (at approximately 8:00 AM on Day -1), complete the following (as listed in [Appendix 2](#)):

- Document the date(s) that excluded medications were discontinued and any other changes to concomitant medications since screening. Record all AEs that occur after the ICF was signed. Verify and ensure PD and sleep medications were taken and continue to be taken at the same dose and regimen. For subjects currently receiving treatment for OSA, review OSA therapy device usage to ensure adequate compliance.
- Administer the ESS Questionnaire.

- Administer the MDS-UPDRS (Parts III and IV). When feasible, the MDS-UPDRS (Parts III and IV) is to be performed on the same study day and approximate same time for each subsequent visit while the subject is in the “on” state.
- Complete the CGIs.
- Perform physical examination.
  - Obtain weight in ordinary indoor clothes (without shoes).
- Obtain vital signs (systolic and diastolic blood pressure [seated and standing], pulse rate [seated and standing], respiratory rate, and body temperature), including at least 2 sets of blood pressure and pulse rate measurements in the seated position after the subject has been resting and seated for at least 5 minutes. Next, standing blood pressure and pulse rate should be taken at 1 and 3 minutes after the subject has been standing.
- 12-lead ECG after the subject has been resting supine for at least 5 minutes.
- If the Baseline visit occurs outside of the screening window (i.e., >29 days after the Screening Visit), obtain safety laboratory blood samples for serum chemistry and hematology tests and a urine sample for urinalysis. Record if the samples were collected with the subject fasted or nonfasted.
- Obtain a urine sample for a pregnancy test for all females of childbearing potential (see [Table 1](#) for definitions of childbearing potential).
- Complete breath alcohol screen test.
- A light breakfast may be served. Breakfast should be completed within 15 to 20 minutes.
- Obtain vital signs (systolic and diastolic blood pressure [seated and standing] and pulse rate [seated and standing]), including at least 2 sets of blood pressure and pulse rate measurements in the seated position after the subject has been resting and seated for at least 5 minutes. Next, standing blood pressure and pulse rate should be taken at 1 and 3 minutes after the subject has been standing.
- Initiate the first trial of the MWT. Before starting the MWT, ask the subject the following question: “How long did you sleep last night?” The first MWT trial should be started approximately 1.5 to 3 hours after the time of the subject arising that morning.
- Obtain vital signs (systolic and diastolic blood pressure [seated and standing] and pulse rate [seated and standing]), including at least 2 sets of blood pressure and pulse rate measurements in the seated position after the subject has been resting and seated for at least 5 minutes. Next, standing blood pressure and pulse rate should be taken at 1 and 3 minutes after the subject has been standing.
- Complete the FSS, Apathy Scale, and SCOPA-cog.
- Administer the C-SSRS Since Last Visit Version and record the results.
- Approximately 2 hours after the start of the first MWT, initiate the second trial of the MWT.
- Subjects should be served a light lunch immediately after the second trial of the MWT.
- After the subject finishes lunch, obtain vital signs (systolic and diastolic blood pressure [seated and standing] and pulse rate [seated and standing]), including at least 2 sets of blood pressure and pulse rate measurements in the seated position after the subject has been resting and seated for at least 5 minutes. Next, standing blood pressure and pulse rate should be taken at 1 and 3 minutes after the subject has been standing.

- Approximately 2 hours after the start of the second MWT, initiate the third trial of the MWT.
- [Optional Assessment] If feasible, approximately 2 hours after the start of the third MWT, initiate the fourth trial of the MWT.
- Review the inclusion and exclusion criteria, including ESS results, to determine the subject's continuing eligibility to participate in the study ([Section 4](#)).
- Randomize to study Treatment Sequence A, B, or C (access IVRS/IWRS).
- Document any AEs that occurred after the ICF was signed.
- Dispense study drug and instruct subject on the daily dose administration to begin on the following morning (Day 1).
- Remind the subject to bring the last dose of their study drug supply to the study center at their next visit. The subject will take their last dose of their study drug supply at the study center during the next visit.
- Schedule the next return clinic visit.

#### 7.2.2 Group 1: Treatment Phase (Day 7 [ $\pm 1$ day], Day 14 [ $\pm 1$ day], Day 21 [ $\pm 1$ day], and Day 28 [ $\pm 1$ day])

The subject may be admitted to the study center the day before the MWT to complete selected assessments (listed in [Appendix 3](#)), provided it falls within the visit window. Individual assessments should be performed on the same study day at approximately the same time of day across study visits.

**Subjects enrolling in the study after Amendment 2 implementation will not undergo PK evaluation.**

On admission to the investigative site in the morning (at approximately 8:00 AM) on Days 7 ( $\pm 1$ ), 14 ( $\pm 1$ ), 21 ( $\pm 1$ ), and 28 ( $\pm 1$ ), complete the following (as listed in Appendix 3):

- Record all concomitant medications, including OTC medications, health, and dietary supplements taken since the last visit. Record all AEs. Verify PD medications, sleep medications allowed by the protocol, and study drug (as specified in [Section 5.3](#) of the protocol) were taken and continue to be taken appropriately. For subjects currently receiving treatment for OSA, review OSA therapy device usage to ensure adequate compliance.
- Administer the ESS Questionnaire.
- Administer the MDS-UPDRS (Parts III and IV). When feasible, the MDS-UPDRS (Parts III and IV) is to be performed on the same study day and approximate same time for each subsequent visit while the subject is in the “on” state.
- Complete the CGIc.
- Perform physical examination.
  - Obtain weight in ordinary indoor clothes (without shoes).
- Approximately 1 hour before dosing, obtain vital signs (systolic and diastolic blood pressure [seated and standing], pulse rate [seated and standing], respiratory rate, and body

temperature), including at least 2 sets of blood pressure and pulse rate measurements in the seated position after the subject has been resting and seated for at least 5 minutes.

Next, standing blood pressure and pulse rate should be taken at 1 and 3 minutes after the subject has been standing.

- 12-lead ECG after the subject has been resting supine for at least 5 minutes.
- Obtain safety laboratory blood samples for serum chemistry and hematology tests and a urine sample for urinalysis.
- Obtain a urine sample for a pregnancy test for all females of childbearing potential (see [Table 1](#) for definitions of childbearing potential).
- Complete breath alcohol screen test.
- Observe study drug administration by the subject.
- Approximately 15 minutes after dosing, subjects may be served a light breakfast. Breakfast should be completed within 15 to 20 minutes.
- Approximately 50 minutes after dosing, obtain vital signs (systolic and diastolic blood pressure [seated and standing] and pulse rate [seated and standing]), including at least 2 sets of blood pressure and pulse rate measurements in the seated position after the subject has been resting and seated for at least 5 minutes. Next, standing blood pressure and pulse rate should be taken at 1 and 3 minutes after the subject has been standing.
- Approximately 1 hour after dosing, initiate the first trial of the MWT. Before starting the MWT, ask the subject the following question: "How long did you sleep last night?" The first MWT trial should be started approximately 1.5 to 3 hours after the time of the subject arising that morning.
- Approximately 2 hours after dosing, obtain vital signs (systolic and diastolic blood pressure [seated and standing] and pulse rate [seated and standing]), including at least 2 sets of blood pressure and pulse rate measurements in the seated position after the subject has been resting and seated for at least 5 minutes. Next, standing blood pressure and pulse rate should be taken at 1 and 3 minutes after the subject has been standing.
- Complete the PGIc, FSS, Apathy Scale, and the SCOPA-cog.
- Administer the C-SSRS Since Last Visit Version and record the results.
- Approximately 3 hours after dosing, initiate the second trial of the MWT.
- Subjects should be served a light lunch immediately after the second trial of the MWT.
- Approximately 4 hours after dosing, obtain vital signs (systolic and diastolic blood pressure [seated and standing] and pulse rate [seated and standing]), including at least 2 sets of blood pressure and pulse rate measurements in the seated position after the subject has been resting and seated for at least 5 minutes. Next, standing blood pressure and pulse rate should be taken at 1 and 3 minutes after the subject has been standing.
- Approximately 5 hours after dosing, initiate the third trial of the MWT.
- Approximately 6 hours after dosing, obtain vital signs (systolic and diastolic blood pressure [seated and standing] and pulse rate [seated and standing]), including at least 2 sets of blood pressure and pulse rate measurements in the seated position after the subject has been resting and seated for at least 5 minutes. Next, standing blood pressure and pulse rate should be taken at 1 and 3 minutes after the subject has been standing.
- Approximately 6 hours after dosing, obtain a 12-lead ECG after the subject has been resting supine for at least 5 minutes.

- [Optional Assessment] If feasible, approximately 7 hours after dosing, initiate the fourth trial of the MWT.
- Document any AEs that occurred since the last visit.
- The safety findings will be reviewed by the investigator, who will decide whether or not to proceed to the next dose.
- Dispense study drug and instruct subject on the daily dose administration to begin on the following morning.
- Complete drug accountability.
- Schedule the next return clinic visit.

### **7.3 Group 2: Baseline and Treatment Phase Study Activities (Subjects Opting Out of the MWT Component of the Study)**

#### **7.3.1 Group 2: Baseline/Randomization/Visit 2 (Day -1)**

After a subject has successfully completed the screening procedures, he or she will return to the investigative site to complete his or her baseline procedures.

On admission to the study center in the morning (at approximately 8:00 AM on Day -1), complete the following (as listed in [Appendix 5](#)):

- Document the date(s) that excluded medications were discontinued and any other changes to concomitant medications since screening. Record all AEs that occur after the ICF was signed. Verify and ensure PD and sleep medications were taken and continue to be taken at the same dose and regimen. For subjects currently receiving treatment for OSA, review OSA therapy device usage to ensure adequate compliance.
- Administer the ESS Questionnaire.
- Administer the C-SSRS Since Last Visit Version and record the results.
- Obtain vital signs (systolic and diastolic blood pressure [seated and standing], pulse rate [seated and standing], respiratory rate, and body temperature), including at least 2 sets of blood pressure and pulse rate measurements in the seated position after the subject has been resting and seated for at least 5 minutes. Next, standing blood pressure and pulse rate should be taken at 1 and 3 minutes after the subject has been standing.
- Perform physical examination.
  - Obtain weight in ordinary indoor clothes (without shoes).
- If the Baseline visit occurs outside of the screening window (i.e., >29 days after the Screening Visit), obtain safety laboratory blood samples for serum chemistry and hematology tests and a urine sample for urinalysis. Record if the samples were collected with the subject fasted or nonfasted.
- Obtain a urine sample for a pregnancy test for all females of childbearing potential (see [Table 1](#) for definitions of childbearing potential).
- Complete breath alcohol screen test.
- A light breakfast may be served. Breakfast should be completed within 15 to 20 minutes.

- Approximately 2 hours after the first set of vital signs are taken, obtain a second set of vital signs (systolic and diastolic blood pressure [seated and standing] and pulse rate [seated and standing]), including at least 2 sets of blood pressure and pulse rate measurements in the seated position after the subject has been resting and seated for at least 5 minutes. Next, standing blood pressure and pulse rate should be taken at 1 and 3 minutes after the subject has been standing.
- Complete the FSS, Apathy Scale, and SCOPA-cog.
- Approximately 1 hour after the second set of vital signs are taken, obtain a third set of vital signs (systolic and diastolic blood pressure [seated and standing] and pulse rate [seated and standing]), including at least 2 sets of blood pressure and pulse rate measurements in the seated position after the subject has been resting and seated for at least 5 minutes. Next, standing blood pressure and pulse rate should be taken at 1 and 3 minutes after the subject has been standing.
- 12-lead ECG after the subject has been resting supine for at least 5 minutes.
- Complete the CGIs.
- Administer the MDS-UPDRS (Parts III and IV). When feasible, the MDS-UPDRS (Parts III and IV) is to be performed at approximately the same time for each subsequent visit while the subject is in the “on” state.
- Review the inclusion and exclusion criteria, including ESS results, to determine the subject’s continuing eligibility to participate in the study ([Section 4](#)).
- Randomize to study Treatment Sequence A, B, or C (access IVRS/IWRS).
- Document any AEs that occurred after the ICF was signed.
- Dispense study drug and instruct subject on the daily dose administration to begin on the following morning (Day 1).
- Remind the subject to bring the last dose of their study drug supply to the study center at their next visit. The subject will take their last dose of their study drug supply at the study center during the next visit.
- Schedule the next return clinic visit.

### 7.3.2 Group 2: Treatment Phase (Day 7 [ $\pm 1$ day], Day 14 [ $\pm 1$ day], Day 21 [ $\pm 1$ day], and Day 28 [ $\pm 1$ day])

Individual assessments should be performed at approximately the same time of day across study visits.

**Subjects enrolling in the study after Amendment 2 implementation will not undergo PK evaluation.**

On admission to the investigative site in the morning (at approximately 8:00 AM) on Days 7 ( $\pm 1$ ), 14 ( $\pm 1$ ), 21 ( $\pm 1$ ), and 28 ( $\pm 1$ ), complete the following (as listed in [Appendix 6](#)):

- Record all concomitant medications, including OTC medications, health, and dietary supplements taken since the last visit. Record all AEs. Verify PD medications, sleep medications allowed by the protocol, and study drug (as specified in [Section 5.3](#) of the

protocol) were taken and continue to be taken appropriately. For subjects currently receiving treatment for OSA, review OSA therapy device usage to ensure adequate compliance.

- Approximately 1 hour before dosing, obtain vital signs (systolic and diastolic blood pressure [seated and standing], pulse rate [seated and standing], respiratory rate, and body temperature), including at least 2 sets of blood pressure and pulse rate measurements in the seated position after the subject has been resting and seated for at least 5 minutes. Next, standing blood pressure and pulse rate should be taken at 1 and 3 minutes after the subject has been standing.
- 12-lead ECG after the subject has been resting supine for at least 5 minutes.
- Perform physical examination.
  - Obtain weight in ordinary indoor clothes (without shoes).
- Obtain safety laboratory blood samples for serum chemistry and hematology tests and a urine sample for urinalysis.
- Obtain a urine sample for a pregnancy test for all females of childbearing potential (see [Table 1](#) for definitions of childbearing potential).
- Complete breath alcohol screen test.
- Observe study drug administration by the subject.
- Approximately 15 minutes after dosing, subjects may be served a light breakfast. Breakfast should be completed within 15 to 20 minutes.
- Approximately 1 hour after dosing, obtain vital signs (systolic and diastolic blood pressure [seated and standing] and pulse rate [seated and standing]), including at least 2 sets of blood pressure and pulse rate measurements in the seated position after the subject has been resting and seated for at least 5 minutes. Next, standing blood pressure and pulse rate should be taken at 1 and 3 minutes after the subject has been standing.
- Administer the ESS Questionnaire.
- Complete the PGIC, FSS, Apathy Scale, and the SCOPA-cog.
- Administer the C-SSRS Since Last Visit Version and record the results.
- Approximately 2 hours after dosing, obtain vital signs (systolic and diastolic blood pressure [seated and standing] and pulse rate [seated and standing]), including at least 2 sets of blood pressure and pulse rate measurements in the seated position after the subject has been resting and seated for at least 5 minutes. Next, standing blood pressure and pulse rate should be taken at 1 and 3 minutes after the subject has been standing.
- Approximately 2 hours after dosing, 12-lead ECG after the subject has been resting supine for at least 5 minutes.
- Complete the CGIc.
- Administer the MDS-UPDRS (Parts III and IV). When feasible, the MDS-UPDRS (Parts III and IV) is to be performed at approximately the same time for each subsequent visit while the subject is in the “on” state.
- Document any AEs that occurred since the last visit.
- The safety findings will be reviewed by the investigator, who will decide whether or not to proceed to the next dose.
- Dispense study drug and instruct subject on the daily dose administration to begin on the following morning.

- Complete drug accountability.
- Schedule the next return clinic visit.

## 7.4 Follow-up (Day 35 [ $\pm 1$ day]) (For Subjects in Both Groups 1 and 2)

At the Follow-up Visit, perform the following:

- Record all concomitant medications, including OTC medications, health, and dietary supplements taken since the last visit.
- Complete physical examination.
  - Obtain weight in ordinary indoor clothes (without shoes).
- Obtain vital signs (systolic and diastolic blood pressure [seated and standing], pulse rate [seated and standing], respiratory rate, and body temperature), including at least 2 sets of blood pressure and pulse rate measurements in the seated position after the subject has been resting and seated for at least 5 minutes. Next, standing blood pressure and pulse rate should be taken at 1 and 3 minutes after the subject has been standing.
- Obtain a 12-lead ECG after the subject has been resting supine for at least 5 minutes.
- Obtain safety laboratory blood samples for serum chemistry and hematology tests and a urine sample for urinalysis.
- Obtain a urine sample for a pregnancy test for all females of childbearing potential (see [Table 1](#) for definitions of childbearing potential).
- Complete breath alcohol screen test.
- Administer the C-SSRS Since Last Visit Version and record the results.
- Complete the ESS Questionnaire.
- Document any AEs that occurred since the last visit. Document the outcome of any ongoing AEs.

Unless any safety issues are identified that require follow-up, the study will be considered completed and the subject will be discharged from the study. Subjects will be instructed to follow-up with their healthcare provider regarding the resumption of any medications that were discontinued prior to study participation.

## 7.5 Early Termination Visit (For Subjects in Both Groups 1 and 2)

If a subject withdraws and is unable or unwilling to take additional study drug, the following safety and final assessments should be conducted.

- Record all concomitant medications, including OTC medications, health, and dietary supplements taken since the last visit.
- Perform a physical examination including a full examination of body systems (excluding a full genitourinary exam) and a brief neurological examination.
  - Obtain weight in ordinary indoor clothes (without shoes).
- Obtain vital signs (systolic and diastolic blood pressure [seated and standing], pulse rate [seated and standing], respiratory rate, and body temperature), including at least 2 sets of blood pressure and pulse rate measurements in the seated position after the subject has

been resting and seated for at least 5 minutes. Next, standing blood pressure and pulse rate should be taken at 1 and 3 minutes after the subject has been standing.

- Obtain a 12-lead ECG after the subject has been resting supine for at least 5 minutes.
- Obtain safety laboratory blood samples for serum chemistry and hematology tests and a urine sample for urinalysis.
- Obtain a urine sample for a pregnancy test for all females of childbearing potential (see [Table 1](#) for definitions of childbearing potential).
- Complete breath alcohol screen test.
- A light breakfast may be served after blood samples are collected.
- Administer the C-SSRS Since Last Visit Version and record the results.
- Document any AEs that occurred since the last visit. Document the outcome of any ongoing AEs.
- Complete drug accountability.
- Schedule a 1-week Safety Follow-up visit, if the subject is willing to continue with follow-up procedures.

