### 6.12 Efficacy Assessments

#### 6.12.1 Epworth Sleepiness Scale

The ESS is a self-administered questionnaire with 8 questions asking the subject how likely they would be to doze off or fall asleep in different situations. Responses range from 0 = would never doze to 3 = high chance of dozing ([Appendix 13](#)). Subjects will be asked to complete the ESS with regard to the level of sleepiness they experienced over the past 7 days at Screening, Baseline; at Visits 3, 4, 5, and 6; and at the Safety Follow-up visit. The ESS provides a measure of a person's general level of sleepiness, or their average sleep propensity in daily life. It is a validated measure with high specificity and sensitivity for assessing subjective sleepiness ([Johns 1991](#); [Broderick et al. 2013](#)).

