### 6.12.5 Clinician Global Impression of Change

The CGIC is a 7-point Likert-type rating scale and a widely used assessment to assess efficacy in clinical drug trials (Appendix 16). Investigators will rate their impression of any change from baseline in the subject's condition on a 7-point scale ranging from 1 = very much improved to 7 = very much worse at Visits 3, 4, 5, and 6.

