### 6.12.6 Patient Global Impression of Change

The PGIC is a 7-point Likert-type rating scale and a widely used assessment to assess efficacy in clinical drug trials ([Appendix 17](#)). Subjects will rate the change from baseline in their condition on a 7-point scale ranging from 1 = very much improved to 7 = very much worse at Visits 3, 4, 5, and 6.

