### 6.14.5 Removal of Subjects from the Trial or Study Drug

All subjects are free to withdraw from participation in this study at any time, for any reason, and without prejudice. The investigator must withdraw any subject from the study if the subject states that he/she wants to stop participating in the study.

The investigator, Jazz Pharmaceuticals or its designee may remove a subject from the study at any time and for any reason.

If any of the criteria below are met during the study, study drug administration must be stopped and the subject must be discontinued from the study.

- Active suicidal ideation or behavior (e.g., a positive response to Question 4 or 5 on the C-SSRS)

- 3-fold or greater elevation above the ULN of ALT or AST accompanied by an elevation of serum total bilirubin greater than 2 times the ULN
- Liver enzyme (AST, ALT) value greater than or equal to 5 times the ULN
- Serum creatinine  $\geq 2$  mg/dL
- Positive urine drug screen (unless due to a prescription medication that is allowed by the protocol)
- Positive pregnancy test
- Subject demonstrates a QTcF interval of  $>450$  msec for males and  $>470$  msec for females (determinations should be based on at least 2 ECG recordings performed in close proximity prior to study drug discontinuation)
- Subject experiences a serious adverse event that is considered related to study drug or procedure

For all subjects who prematurely discontinue, an attempt should be made to perform all early termination assessments as indicated in [Section 7.6](#). Subjects should be asked to return 1 week later for a Safety Follow-up visit.

The specific reason for the discontinuation should be documented on the termination eCRF. If a subject withdraws informed consent, the specific reason for withdrawing the informed consent should be stated.

Adverse events resulting in termination will be followed to the satisfactory resolution and determination of outcome as ascertained by the investigator (and/or Jazz Pharmaceuticals or its designee). The data will be recorded on the appropriate eCRF.

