#### 6.14.6 Handling of Early Terminations

If a subject terminates early from the study, either at his or her request or at the investigator's discretion, the investigator will record the reason(s) for early termination on the relevant eCRF page and notify the medical monitor immediately. All subjects who terminate from the study early should undergo all Early Termination visit assessments as described in [Section 7.5](#).

It is vital to obtain follow-up data on any subject who terminated because of an AE, abnormal laboratory test, or ECG finding. In any case, every effort must be made to undertake safety follow-up procedures.

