## 7.6 Discontinuations

If a subject is withdrawn before completing the study, the reason for withdrawal will be entered on the appropriate eCRF. The specific reason for the withdrawal should be documented on the eCRF. For instance, rather than stating “withdrew informed consent,” the specific reason for withdrawing the informed consent should be stated. Whenever possible and reasonable, the evaluations that were to be conducted during the final study visit should be performed at the time of premature discontinuation.

It is vital to obtain follow-up data on any subject who terminated because of an AE, abnormal laboratory test, or ECG finding. In any case, every effort must be made to ensure safety follow-up procedures are completed.

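### For subjects who stop between scheduled visits, Protocol 7.5 schedules no on-dose ESS, CGIc or PGIc, in conflict with 7.6, and SAP Table 4 sends an ESS taken after the last dose to a window outside the model

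*Protocol*

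**What the plan says.** **Early Termination list.** Protocol 7.5 states that "the following safety and final assessments should be conducted". The items are concomitant medications, physical examination and weight, vital signs, ECG, laboratory tests, pregnancy test, breath alcohol, C-SSRS, adverse events and drug accountability. The ESS row is blank under ET in Protocol Appendices 1 and 4 and in SAP Table 2.

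**Timing of the scales.** Protocol 6.12.1 schedules the ESS "at Screening, Baseline; at Visits 3, 4, 5, and 6; and at the Safety Follow-up visit". Section 6.12.5 has the CGIc rated on a scale "ranging from 1 = very much improved to 7 = very much worse at Visits 3, 4, 5, and 6", and Section 6.12.6 sets the PGIc at the same visits. None of the three sections names Early Termination.

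**A different instruction.** Protocol 7.6 says that, where possible and reasonable, "the evaluations that were to be conducted during the final study visit should be performed at the time of premature discontinuation".

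**Cross-references.** Section 6.14.5 says "an attempt should be made to perform all early termination assessments as indicated in" Section 7.6. Section 6.14.6 says "All subjects who terminate from the study early should undergo all Early Termination visit assessments as described in" Section 7.5.

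**End-of-period visits.** Protocol 7.2.2 and 7.3.2 list ESS, CGIc and PGIc at Visits 3 to 6, ahead of this step: "The safety findings will be reviewed by the investigator, who will decide whether or not to proceed to the next dose".

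**Analysis.** SAP 6.3 maps Early Termination data to visit windows. In SAP Table 4, for a subject who takes no later drug, the period window closes on the day of the last dose. The Safety Follow-up window opens the next day and can stretch to the Early Termination visit. SAP 16.1.4 excludes follow-up data from the ESS model, and SAP 16.1.3 does not impute a missing ESS total.

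**The concern.** Active doses only ascend, and subjects who do not tolerate the drug are considered for early termination. A subject who stops part-way through a week is therefore likely to differ from those who finish it. If no ESS is recorded on that dose, the estimate for the dose rests on those who stayed and on the mixed model's missing-at-random assumption. None of the sensitivity analyses in SAP 16.1.5 addresses dropout; they cover carry-over, treatment-by-sequence interaction and analysis population.

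There is also a problem of conduct. Two sites can both follow the protocol and collect different data from the same kind of withdrawal, because the two cross-references lead to different lists. The SAP expects Early Termination data, yet its own window would discard an ESS taken the day after the last dose.

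**Working it through.** **1. The two routes side by side.**

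| Route | Leads to | ESS | CGIc and PGIc |
|---|---|---|---|
| 6.14.6 | 7.5 | no | no |
| 6.14.5 | 7.6, final visit read as Visit 6 | yes | yes |
| 6.14.5 | 7.6, final visit read as Visit 7 | yes | no |

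The protocol does not define *final study visit*. Sections 6.4 and 6.8 pair Early Termination with Visit 6, but subjects are discharged at Visit 7 (3.1, 7.4). Section 7.5 falls short of 7.6 on either reading. In the text as read, the CGIc row of Appendix 1 looks displaced by one column, and the ET and follow-up columns of SAP Table 3 are merged; nothing here rests on either.

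**2. Who is affected.** A subject stopped at Visit 3, 4 or 5 has all three scales on the current dose before the decision is made. A subject who stops between visits has none scheduled on that dose under 7.5.

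**3. Where an Early Termination ESS would fall.** Example: Period 3 starts on Day 15 and the last dose is on Day 18. The Week 3 window is Days 15 to 18. Follow-up runs from Day 19 to the later of Day 26 and the Early Termination visit. An ESS on Day 18 enters the model. An ESS on Day 19 does not.

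**4. The plan's own figures.** Allocation is 21:21:7, with 34 completers expected in Sequences A and B: (42 − 34)/42 = 8/42 = 19.0%. The stated power is 80% for a 3-point difference with SD 6 and 2-sided 0.05. Taking 6 as the SD of the within-subject difference (common SD 6, correlation 0.5), the noncentrality is 3/(6/√34) = 2.92 on 32 degrees of freedom. Power is 80.7%, so the figure reproduces.

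**5. Bias in a raw 300 mg mean.** Assume a true effect of −3 in those observed and 3 points worse (no effect) in those lost.

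- 8 lost: (34 × −3 + 8 × 0)/42 = −2.43, against −3 observed. The difference is 0.57 = (8/42) × 3.
- 2 lost: (2/42) × 3 = 0.14.

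**6. Bias in the planned model.** The inputs are fixed treatment, period and sequence, a random subject effect, SD 6 with correlation 0.5 (variance 18 between and 18 within subjects), allocation 21:21:7, and a true 300 mg difference of −3. The baseline covariate is left out. Eight subjects are removed from their 300 mg period onward (Period 4 in A; Periods 3 and 4 in B) and are 3 points worse in every period they have. The expected estimate is the generalized least squares solution (ΣX′V⁻¹X)⁻¹ΣX′V⁻¹μ over subjects.

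| Losses in A / B | Expected 300 mg effect | Departure from −3 |
|---|---|---|
| 4 / 4 | −3.03 | 0.03 too favourable |
| 8 / 0 | −3.19 | 0.19 too favourable |
| 0 / 8 | −2.87 | 0.13 too unfavourable |

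The largest departure depends on the correlation: about 0.3 at correlation 0.3 and about 0.1 at 0.7.

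If the 3-point deficit appears only on 300 mg, earlier periods carry no trace of it. The model then returns −3.00 while the average over all 42 is −2.43, a gap of 0.57.

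**The case against.** The strongest reply is that little is lost. The protocol's built-in decision point comes after the scales have been completed on the current dose. The ESS is also collected at Safety Follow-up if the subject attends, and SAP 16.1.4 summarizes it. The model keeps every earlier period. Safety is the primary objective, and ESS p-values are nominal (SAP 16.1.2). An Early Termination ESS is also an impure measure: with a 7-day recall, a subject stopping on Day 2 of 300 mg gives a score of which only about 2/7 reflects that dose.

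Most of this stands, and it limits the point without removing it. The follow-up ESS is taken about a week off drug and is outside the model. Earlier periods help only so far as they predict the missing one. The recall problem argues for a restricted sensitivity analysis; it does not justify leaving the scales out.

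Two stronger readings are tempting:

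- A reader might infer that the key endpoint is never observed on the dose that led to withdrawal. The documents do not support this: subjects stopped at an end-of-period visit have it, and a site following 7.6 may collect it.
- A reader might infer that the 300 mg effect is overstated by 0.57 points, 19% of the 3-point target. That is a raw-mean worst case. It needs every planned non-completer to stop mid-period on 300 mg, and the planned model reproduces it only if the deficit is specific to that dose.

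**Conclusion.** The point holds for subjects who stop between scheduled visits. Section 7.5 and the ESS row of the ET column schedule no on-dose sleepiness outcome for them. This contradicts 7.6, the two cross-references disagree, and SAP Table 4 would exclude an ESS taken after the last dose.

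The likely size is small. With all 8 of 42 lost from 300 mg onward, the bias is about 0.03 to 0.2 points in either direction if they are 3 points worse throughout (at correlation 0.5), and up to 0.57 only if the deficit is specific to 300 mg. The count is an upper bound, because the eight would also include stops on other treatments and at scheduled visits. The 3-point deficit is an assumption, and the results scale with it. The documents give neither the number of mid-period stops nor the outcomes of those who stop.

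This is a correction worth making because it is cheap and removes an internal contradiction. It does not undermine the key efficacy analysis.

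**What to change.** **Protocol.** Add ESS, CGIc and PGIc to Section 7.5 and to the ET column of both schedules of events. Define *final study visit* in 7.6. Make 6.14.5 and 6.14.6 cite the same list.

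**SAP.** In Table 4, assign an Early Termination efficacy assessment taken within 1 day of the last dose to the period of that dose. Use it in a sensitivity analysis of the ESS model, not in the main model by default. Restrict that analysis to subjects with a stated minimum number of days on the dose, because of the 7-day recall, and report the model with and without these values.

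**Cost.** Amendment wording, a few minutes of questionnaires at a visit that already takes place, and one extra model run. The change does not recover periods a subject never reaches; in Sequence B that includes the placebo week.
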